	
positive at or before the 300 mg (443 mg cumulative) dosing level of FA protein. OIT treatment groups will be cashew or shrimp.
 
All cohorts will undergo an updosing regimen starting at 5 mg allergen, with dose escalation every 2 weeks to reach a 1,000 mg dose at week 28, after which they will be maintained at that dose for 24 weeks. At the conclusion of the maintenance phase (Week 52), participants will undergo DBPCFC. Participants that pass their food challenge with no or mild objective reactions to up to a cumulative 2043 mg of the FA allergen in their OIT at the end of this phase (primary outcome) will be considered desensitized and have successfully met the primary endpoint.
 
All participants then will continue in the study by undergoing a withdrawal from OIT for 6 weeks to examine mechanisms underlying sustained responsiveness (SU) which will be defined as a participant’s passing DBPCFC with no or mild objective reaction to up to a cumulative 2043 mg of the FA allergen in their DBPCFC at week 58. Those participants who pass the Week 58 challenge up to a cumulative of 2043 mg will be given the option to continue the withdrawal phase up to Week 64 which will be end of study. Week 58 will be end of study for those who do not opt for this continuation of withdrawal.

Primary Endpoint(s)
	
Change in expression of CD28 in the CD4+ allergen specific (CD154+) T-cells at 52 weeks relative to baseline values between those who do and do not tolerate a cumulative of 2043 mg in the DBPCFC at week 52.

Secondary Endpoint(s)
	
 • Compare changes in expression of CD28+ allergen specific (CD154+) T-cells over multiple time points from baseline to week 58 and week 64 between those with sustained unresponsiveness (SU) vs those desensitized but SU failures vs those who did not pass the desensitization DBPCFC • Compare changes in the following measures in CD4+CD28+ allergen specific (CD154+) T-cells at week 52 and week 58 between those who achieved sustained unresponsiveness (SU) vs those desensitized but SU failures vs those who did not pass the desensitization DBPCFC at week 52. 
 ○ Levels of IFN-gamma ○ Levels of IL-4 ○ Receptor diversity in allergen specific T cell CDR3b as compared to non-specific T cells ○ Levels of IL-10 ○ Levels of TGF beta ○ Levels of GPR15 ○ Levels of CCR4+ ○ Levels of CRTh2

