Updosing phase (Week 1 to Week 28): All cohorts will undergo an updosing regimen starting at 5 mg allergen, with dose escalation every 2 weeks to reach a maximum maintenance dose of 1000 mg dose at Week 28. We expect active OIT treatment subjects to reach 1000 mg of allergen protein (cashew or shrimp) between 26 to 28 weeks. Participants who have not reached 1000 mg by week 28 will continue to be up dosed, if considered safe, until week 52. In case of unforeseen circumstances that make an in-person visit in clinic difficult, doses may need to be sent to the participant’s home.

Maintenance phase (Week 28 to Week 52): Once participants get to the 1000 mg dose at week 28, they will stay on that dosage until Week 52. At week 52, participants will undergo DBPCFC. Participants that pass their food challenge with no or mild objective reactions to up to a cumulative 2043 mg of the FA allergen in their OIT at the end of this phase (primary outcome) will be considered desensitized and have successfully met the primary endpoint.

Withdrawal phase (Week 52 to Week 58 and Optional Week 64): Withdrawal from OIT will occur for 6 weeks, from week 52 to week 58 for all participants (Refer to Appendix 2 for participant disposition). This withdrawal phase is designed to examine mechanisms underlying sustained unresponsiveness (SU). SU will be defined as a participant’s

passing a DBPCFC with no or mild objective reaction to up to a cumulative 2043 mg of the FA allergen in their OIT at week 58. We chose a 6-week period of withdrawal based on prior studies (Andorf et al, 2018, Burks, et al. New England Journal of Medicine, 2012). If the participant passes the Week 58 DBPCFC up to a cumulative of 2043 mg, he/she will be given the option to continue avoidance until Week 64 and perform another set of DBPCFCs to further assess SU.

End of study (Week 58 or Week 64): Participants will be followed until week 58 or until Week 64 for those who choose to continue avoidance beyond Week 58). Participants will be given guidance on how to consume real food equivalents based on their current tolerated dose. (Appendix 2).

Participant Disposition (see Appendix 2):

Any participant that at least can tolerate 300 mg of FA protein will continue to dose at 300 mg and will be asked to come back at week 52, and 58 for blood and/or skin tests.

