300mg, 600mg, 1000mg and 2000mg. . Both food allergens (cashew or shrimp) and oat protein will be concealed in a food that masks the taste. After the last dose of the DBPCFC, the subject will be monitored for 2 hours and then discharged home. Subjects will be considered to have tolerated the OFC if they do not experience any objective reactions by Appendix aa.

If the subject experiences reactions, they will be treated with the necessary rescue medications. They will be observed for a minimum two hours after the final administered dose and discharged home only when deemed clinically stable by a study physician.

After the Week 52 DBPCFC, subjects who meet the following criteria will discontinue FA protein daily dosing entirely:

- On OIT treatment for 52 weeks,
- Taking daily maintenance dose of 1000 mg protein for approximately 3 weeks,
- No severe reactions (CoFAR criteria) to home dosing, and/or

Subjects who do not pass a cumulative of 2043 mg at Week 52 will be considered desensitization failures. They will be considered in statistical analyses of the intent-to-treat population. They will be followed until the end of study (week 58).

After Week 52, all subjects will begin their withdrawal phase for 6 weeks.

On Study DBPCFC (Week 58, Week 64): At Week 58 subjects will have a DBPCFC to up to 4043 mg to assess sustained unresponsiveness (tolerance). The visit will also include a physical assessment, spirometry, fecal matter collection, skin prick test, and blood draw for mechanistic studies.

During the oral food challenge, there should be increased hydration (i.e. about 16 oz or more given orally). There are no published data indicating whether repeating food challenges every 6 weeks will or will not maintain desensitization or otherwise affect the outcomes in this study. Our preliminary studies in which we have performed DBPCFCs every 3 months in a separate phase 1 study cohort (n=87 subjects) have demonstrated no increased risk of sensitization (as per repeat cumulative doses on repeat DBPCFC and as per severity of reaction).

End of study (Week 58 or Week 64): Participants will be followed until week 58 or until Week 64 if they opt to continue avoidance of OIT for 8 more weeks after Week 58.

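### Section 8.3 contradicts itself, the synopsis and 3.1 on who stops OIT after week 52, and the formal SU classification has no off-treatment condition to catch anyone still dosing

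*Combined protocol and SAP*

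**What the plan says.** Statements on who stops OIT:

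- **Everyone stops.** Synopsis, Study Design: "All participants then will continue in the study by undergoing a withdrawal from OIT for 6 weeks". Section 3.1, withdrawal phase: "Withdrawal from OIT will occur for 6 weeks, from week 52 to week 58 for all participants". Section 8.3: "After Week 52, all subjects will begin their withdrawal phase for 6 weeks". The synopsis treatment description also makes the week-52 challenge the end of the intervention.
- **Those meeting a list stop.** Section 8.3: "After the Week 52 DBPCFC, subjects who meet the following criteria will discontinue FA protein daily dosing entirely". The list has three items: 52 weeks on OIT; "Taking daily maintenance dose of 1000 mg protein for approximately 3 weeks"; and "No severe reactions (CoFAR criteria) to home dosing, and/or". It breaks off there and does not say what happens to anyone who does not qualify.
- **Some continue.** Section 3.1, participant disposition: "Any participant that at least can tolerate 300 mg of FA protein will continue to dose at 300 mg". They return at weeks 52 and 58 for blood or skin testing. No stop date is given.

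Statements on SU:

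- The Study Definitions Page requires a pass at the week-58 challenge and does not mention being off OIT.
- The synopsis and 3.1 define SU in the same terms, but in the text describing the withdrawal phase.
- The safety wording (synopsis, 2.4, 3.5, 13.2.2) does place the week-58 challenge after six weeks off OIT.
- Section 13.4.4 sorts participants into three classes (not desensitized, desensitized without SU, SU) and has no rule for someone who did not stop.

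**The concern.** SU is meant to describe tolerance that persists once treatment has been withdrawn. A participant who is still taking the allergen daily and passes at week 58 has shown desensitization on therapy, which is a different state. The plan expects the two states to differ immunologically (section 9 tabulates separate expected results for each), and the secondary endpoints in 3.3 compare the SU, SU-failure and non-desensitized groups on CD28 and the other markers. On-treatment passers inside the SU group would raise the SU proportion and blur the contrast that the withdrawal phase exists to examine.

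There is also a practical problem. Two of the conflicting instructions sit in the same subsection of 8.3, so site staff cannot tell from the text whether a participant who misses the list stops or carries on.

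**Working it through.** The plan states no power or sample size figure for SU, so there is none to reproduce. The check is a reconciliation of the text, with two short calculations.

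**1. Does the criteria list exclude anyone?** That depends on the unfinished conjunction.

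- If the items are alternatives, anyone on OIT for the full 52 weeks qualifies on the first item alone. The list then agrees in effect with universal withdrawal.
- If all items must hold, three groups that the protocol allows to remain on treatment can miss it: late reachers, because 3.1 lets updosing run to week 52; maintenance failures, whose last tolerated dose below 1000 mg is accepted under 6.4.2; and participants with a severe home reaction handled by dose reduction, also allowed by 6.4.2.

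**2. How late must a late reacher be?** In Table 2 of section 8.3, dose k starts at week 2(k − 1).

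- On schedule, 1000 mg is dose 14 and starts at week 2 × 13 = 26, which leaves 52 − 26 = 26 weeks at that dose.
- Eleven two-week delays: start at week 26 + 22 = 48, with 4 weeks at 1000 mg.
- Twelve two-week delays: start at week 26 + 24 = 50, with 2 weeks, short of the listed 3.

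Missing the list by this route is possible but needs long delays. Maintenance failures below 1000 mg miss it whatever the timing.

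**3. Would a participant still dosing be classed as SU?** The week-58 challenge in 8.3 is for subjects without an off-OIT condition. The definitions-page entry needs only the pass. Under 13.4.4, a participant who passed at week 52 and passes again at week 58 falls in the SU class.

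**4. Illustration of size.** Let f be the share of desensitized participants still dosing and p the true SU rate. Assume those still dosing are a random draw and all pass.

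- Observed SU = p(1 − f) + f
- Share of the SU group on treatment = f / [p(1 − f) + f]

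The 58 desensitized come from the planning assumption in 13.7 (81% of 72). Both f and p are assumptions, since the documents give neither.

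With p = 50%:

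| f | Still dosing, of 58 | Observed SU | SU group on treatment |
|---|---|---|---|
| 5% | 2.9 | 52.5% | 9.5% |
| 10% | 5.8 | 55% | 18% |
| 20% | 11.6 | 60% | 33% |

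Counting exactly six people gives (52 × 0.5 + 6)/58 = 32/58 = 55%, with 6/32 = 19% of the SU group on treatment. Over p from 30% to 70%, the on-treatment share runs from 7% (f = 5%, p = 70%) to 45% (f = 20%, p = 30%).

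**The case against.** The strongest reply is that the intent is clear. The synopsis, 3.1 and 8.3 each withdraw everyone. The visit schedules in Figure 2 and Appendix 1 mark no OIT at weeks 52, 58 or 64. Section 3.1 offers week-58 passers the option of continuing avoidance, which presumes they are already off treatment. The list never says that non-qualifiers keep dosing. All of this stands, and it makes universal withdrawal the likely reading. It does not remove the conflict, because a list of conditions for stopping has no function if everyone stops.

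A reader might infer four stronger things that the documents do not support:

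- **That SU is nowhere tied to being off OIT.** It is, in the safety wording and by context in the synopsis and 3.1. The gap is in the definitions-page entry and in 13.4.4.
- **That participants held at 300 mg would be counted as SU.** The sentence says they "will continue to dose at 300 mg and will be asked to come back at week 52, and 58" and names only blood or skin testing at those visits. With week 52 still ahead of them, it reads as disposition of people whose updosing stopped early. On its own terms it produces no week-58 pass. Appendix 2, which 3.1 and 8.3 cite for disposition, may hold a figure that is not visible in the text reviewed, so this sentence cannot be judged fully.
- **That three weeks at 1000 mg contradicts the planned 24-week maintenance.** It need not. Updosing may run to week 52, so a short minimum for late reachers is coherent.
- **That six participants still dosing would lift SU from 50% to 60%.** Starting from 29/58, that needs (29 + 6)/58 = 35/58, so all six would have to be people who fail once off treatment. A random six gives 55%.

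**Conclusion.** The contradiction is real, and the passages must be reconciled. Its statistical consequence is conditional: it arises if the criteria list is applied with all items required, if some participants who passed at week 52 miss it and keep dosing, and if they then pass at week 58. The number affected is not in the documents. Figures such as 55% observed SU with about 18% of the SU group on treatment rest on the assumed f, p and full pass rate shown in the working.

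The primary analysis compares CD28 change at week 52, before withdrawal begins, and is unaffected. What is touched is the secondary and exploratory SU comparisons, which 13.4.4 and 13.4.5 already describe as hypothesis generating. Severity is moderate. No view is taken here on which stopping rule is clinically right.

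**What to change.** 1. Reconcile 3.1 (including the 300 mg sentence and its missing stop date), 8.3 and Appendix 2 to a single statement of who stops OIT at week 52. Which rule applies is the sponsor's clinical decision. If the criteria list is kept, complete it, state whether all items or any one must hold, and say what happens to those who do not meet it.
2. Carry the off-treatment condition that the safety endpoints already use into the SU entry on the Study Definitions Page and into the 13.4.4 phenotype classes.
3. State in 13.4.4 that anyone still dosing at week 58, or without a week-58 challenge, is reported separately from SU, with counts.

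The cost is wording in the protocol and analysis plan. No visit or assay is added, and at most a few participants would move out of the SU group.

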8.4. Unscheduled Visits

If disease activity increases or other concerns arise between regularly scheduled visits, participants should be instructed to contact study personnel and may be asked to return to the study site for an “unscheduled” visit.

Unscheduled visits may be performed for significant food allergy episodes which may be reported by the subject between regularly scheduled visits. Significant food allergy episodes are defined as those for which epinephrine is administered based on criteria in the subject’s Food Allergy Action Plan. Unscheduled visits may include physical assessment, blood draw and/or skin prick test. Review of the circumstances around the episode and appropriate documentation of the adverse event will be recorded in the study chart.

8.5. Visit Windows

Study visits should take place within the time limits specified below: the designated visit windows (i.e. +/- n days) for each scheduled visit are also indicated on the Table of Events.

Table 3: Visit Windows*

Visit Type	Target Date	Visit Window
------------	-------------	--------------

Screening/Baseline/Randomization	Day -364 to 1	Day -364 to Day 1
Initial dose day	Day 1	Within 364 days from screening
Dose Escalation Phase	Weeks 2, 4, 6, 8, etc. until maintenance dose is reached	±7 days
Maintenance Phase	Weeks 28 to 52	
Tolerance Phase	Weeks 52 to 58 and up to optional Week 64	

* in the time of an epidemic, doses might need to be sent to the participant’s home at the same dose.

9. Mechanistic Assays

Comparisons for each of the parameters discussed below could occur between:

- On Treatment vs. Baseline for each participant, and
- SU vs. Desensitized but SU Failures clinical outcomes at week 58 DBPCFC.
- Desensitized vs all others at week 52 DBPCFC

I) Serum Assays

Serum Assays

Panel	Volume needed for each sample collection
Specific IgE, IgG4, IgA anti-food allergen and the component-resolved testing where applicable	1 ml
Epitope Arrays	350 microliters

Expected Results for Serum Parameters

Parameter	Desensitization	SU
Specific IgE And Specific IgG4	Progressive decrease in specific IgE to food allergen (FA) and increase in specific IgG4	Low specific IgE and increased IgG4
Epitope Array for IgE for FA peptides— predictive marker for outcome	Progressive Inhibitory antibodies present in epitope array	Intermediate epitope spreading at baseline
Specific IgA	Progressive increases in specific IgA over time	Intermediate levels of specific IgA

Note: Compared to placebo, in which we assume no changes will occur.

II) Cell components for CyTOF

Expected Results for Cell Parameters

Parameter	Desensitization	SU
Th2	Progressive decrease in Th2 absolute numbers and ICS transcription factors and Th2 cytokines	Low Th2 cells and low ability to proliferate in response to FA
Anergy	Decreased CD28 and CD38	Lack of CD28 and CD38
Th1	Progressive increase in Th1 absolute numbers and ICS transcription factors and Th1 cytokines	High Th1 cell numbers and ability to proliferate in response to FA
Th17	Do not expect change	Do not expect change
Treg	Progressive increase in absolute counts of Treg but then decline by 12 mo.	Intermediate Treg cell numbers and decreased ability to proliferate in response to FA
NKT	Progressive increase in absolute counts of NKT cells	Intermediate NKT cell numbers associated with desensitization
DC	Progressive decrease of TSLP receptor in mDCs, progressive increase in CD103 and CCR9 in DCs	Intermediate TSLP receptor expression in mDCs and intermediate DC expression of CD103 and CCR9
Cell death markers	Progressive increase in cell death of allergen-specific Th2 memory cells	Intermediate cell death of allergen-specific Th2 memory cells
Chemokine receptors	Progressive increase in CCR4 and CCR8 in Treg	Intermediate expression of CCR4 and CCR8 in Treg
Allergen specific cells	Switch from mostly Th2 to Th1 or Treg	Intermediate decrease in Th2

	subset over course of therapy	cytokines and transc. factors
--	-------------------------------	-------------------------------

Note: Compared to placebo, in which we assume no changes will occur.

III) Sample Basophil Assay:

Expected Results for Basophil Activation Parameters

Parameter	Desensitization	SU
CD203c/CD63	During course of therapy, will see decrease in basophil reactivity sooner than lowering of specific IgE in participants	Basophil reactivity decreases.

Logistics: We will collect up to 30 mL on any one blood draw not to exceed 5ml/kg over a 12 week period These volumes are more conservative than Stanford IRB limitations (3ml/kg over a 12-week period) and NIH guidelines (for children: 5 ml/kg at any single draw, no more than 9.5 ml/kg over an 8-week period; for adults: the smaller of 10.5 ml/kg or 550 ml total at any single draw)...

10. Biospecimen Storage

Biospecimen storage will occur in the [name] laboratory using a previously validated and published storage procedure for samples (available upon request).

11. Criteria for Participant and Study Completion and Premature Study Termination

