4.1. Rationale for Study Population

This is a single site study to be conducted at the Sean N Parker Center for Allergy and Asthma Research at Stanford University. We will limit our age group to 7-55 years so that we may collect adequate blood volumes for mechanistic studies. The upper age limit of 55 years was selected to reduce the risk that the patients have undiagnosed, underlying

cardiovascular conditions that could entail significant risk with the use of epinephrine in subjects exposed to the risk of anaphylaxis.

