For specific questions related to dosing escalation or continuation of the same dose that are not answered in the above protocol, the PI will be available for questions and decision-making.

If, at any point in the study, the subject complains of new onset vomiting, dysphagia, chronic abdominal pain, and/or difficulty swallowing for more than 2 weeks despite use of daily anti acids (<https://www.webmd.com/heartburn-gerd/qa/what-are-examples-of-antacids>), the subject will be given daily proton pump inhibitors (dosed per age and weight) <https://medlineplus.gov/ency/patientinstructions/000381.html> and if no relief occurs in 2 weeks, they will be referred to a gastroenterologist for assessment of possible gastroenterological disorders associated with food allergy (i.e., eosinophilic esophagitis). If at any point, side effects develop from the use of antacids or PPIs, the subject will be discontinued for the concomitant medication and referred to a GI specialist.

Any subject who discontinues build-up dosing due to repeated allergic reactions to the characterized food allergen will have his/her blood drawn for mechanistic studies within approximately 1 week of discontinuation of therapy.

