8.2. Screening/Baseline Visit

The purpose of the screening period is to confirm eligibility to continue in the study. The Screening/Baseline assessments may take place over several visits. Baseline/screening visits following requirements below, conducted under a different protocol (Screening Protocol) can be used towards this study.

All assessments must be completed no more than 40 weeks (Appendix 1) preceding initiation of FA treatment.

The following procedures, assessments, and laboratory measures will be conducted to determine participant eligibility:

- Consent and assent
- Medical history, including review of all food allergies
- Review of medications participants are currently taking
- Physical assessment
- Pregnancy test, if subject is a female who has undergone menarche and is of childbearing potential (i.e., not otherwise incapable of having children from a previous medical condition, surgery, or other circumstance)
- Blood draw for allergen-specific IgE and IgG4 measurement, lab tests and research samples
- Skin prick test to FA extract (neat extract with no dilution, Greer Laboratories, Lenoir, NC)
- Spirometry and/or Peak Expiratory Flow (PEF)
- Stool sample collection
- DBPCFC to a 443 mg cumulative total allergen protein

Any of the above items may be repeated within the 40 weeks preceding initiation of study treatment if warranted, in the opinion of the investigator, by changes in the subject's clinical status.

Double-Blind Placebo-Controlled Food Challenge (DBPCFC) at Screening

Randomization and preparation of the challenge materials will be performed by trained study personnel in the GMP facility at Stanford. Prior to the food challenge, subjects will be asked to restrict the use of oral antihistamines (five half-lives), beta-agonists (12 hours), theophylline (12 hours), and cromolyn (12 hours).

Subjects will not have active wheezing, spirometry demonstrating FEV1 <80% predicted, or a current flare of atopic dermatitis that contraindicates dosing in the clinical judgment of the study physician. If the participant is unable to perform spirometry, a peak expiratory flow \geq 80% predicted and clear breath sounds on a lung examination will be used to determine if an oral food challenge can be performed.

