11.4. Follow-up after Early Study Withdrawal

Subjects who prematurely discontinue treatment with OIT may remain in the study until end of study visit at week 58 to monitor safety and efficacy parameters. These visits will include skin testing and/or a blood draw for mechanistic studies at the study time points.

If the subject refuses this follow-up, or begins and then elects to discontinue the follow-up, they will be asked to come in for a final study visit consisting of a physical assessment, skin test, blood draw, review of their Food Allergy Action Plan, and instructions to discontinue any OIT dosing and continue food allergen avoidance.

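### Section 9 calls its 12-week blood cap more conservative than the cited IRB limit, but the cap is 67% higher, so the written rule lets light participants exceed that limit

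*Combined protocol and SAP*

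**What the plan says.** The Logistics paragraph at the end of section 9 sets two limits: "We will collect up to 30 mL on any one blood draw not to exceed 5ml/kg over a 12 week period". The next sentence compares them with outside rules: "These volumes are more conservative than Stanford IRB limitations (3ml/kg over a 12-week period", followed by NIH limits. For children these are 5 ml/kg at a single draw and 9.5 ml/kg over 8 weeks; for adults, the smaller of 10.5 ml/kg or 550 ml at a single draw. No other section states or corrects a blood cap.

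The Schedule of Events (Appendix 1) lists blood for T cell studies at screening, week 0, week 52, week 58 and optional week 64. The footnote to the flow chart in section 3.1 accepts a sample from either screening or week 0 if both cannot be done. Other draws are possible:

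- Screening (section 8.2): "Any of the above items may be repeated within the 40 weeks preceding initiation of study treatment if warranted", by a change in clinical status.
- Unscheduled visits (section 8.4): "Unscheduled visits may include physical assessment, blood draw and/or skin prick test".
- Participants who stop build-up because of repeated reactions (section 6.4.2): "will have his/her blood drawn for mechanistic studies within approximately 1 week of discontinuation of therapy".
- Follow-up after stopping treatment (section 11.4): "These visits will include skin testing and/or a blood draw for mechanistic studies at the study time points".

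Eligibility starts at age 7, with no minimum weight (section 4.2). Section 4.1 ties the age range to blood volume: "We will limit our age group to 7-55 years so that we may collect adequate blood volumes for mechanistic studies".

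**The concern.** The cap is an operative limit that protects participants, including children, and the text presents it as stricter than the IRB rule when the printed figures say the reverse. Section 16.1 makes the protocol the document that the IRB reviews and approves, so the reassurance goes to the body whose limit is cited. Site staff who follow the cap as written could take more research blood from a small child than the cited limit allows and still comply with the protocol. The age range was chosen with blood volume in mind, but no weight rule follows from that choice.

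**Working it through.** **Inputs.** From section 9: at most 30 mL per draw; study cap 5 ml/kg per 12 weeks; cited IRB limit 3 ml/kg per 12 weeks. From Appendix 1: the timing of scheduled draws. Body weight W (kg) and actual draw size v (mL) are not in the documents and are assumptions here.

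**1. The stated comparison.** 5/3 = 1.67. The cap is 67% higher than the IRB limit, so the statement that it is more conservative cannot be reproduced. The largest excess the cap permits is 5 − 3 = 2 ml/kg.

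**2. When the written rule permits more than 3 ml/kg.** With n full draws in one 12-week window the total is 30n mL. It exceeds 3W when W < 30n/3 = 10n kg, and the 5 ml/kg cap allows it in full when W ≥ 30n/5 = 6n kg.

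- One draw: exceeds 3 ml/kg only below 10 kg.
- Two draws: below 20 kg (allowed in full from 12 kg).
- Three draws: below 30 kg (allowed in full from 18 kg).

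**3. Size.** Permitted excess = max(0, min(30n, 5W) − 3W).

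| W (kg) | 3W (mL) | Two draws: excess | Three draws: excess |
|---|---|---|---|
| 18 | 54 | 60 − 54 = 6 mL | 90 − 54 = 36 mL |
| 20 | 60 | 0 | 90 − 60 = 30 mL |
| 25 | 75 | 0 | 90 − 75 = 15 mL |
| 30 | 90 | 0 | 0 |

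For smaller draws the threshold is nv/3. With v = 20 mL it is 13.3 kg for two draws and 20 kg for three; with v = 10 mL, 6.7 and 10 kg.

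**4. How many draws can fall in 12 weeks.** Weeks 52 and 58 are 42 days apart, so two are scheduled. A third is contingent:

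- Week 64 is exactly 84 days after week 52, so it shares the window only if both end days count and visits are on target. It also requires passing the week 58 challenge and choosing to go on; section 3.1 says such a participant is "given the option to continue avoidance until Week 64 and perform another set of DBPCFCs to further assess SU". The end-of-study paragraph of section 8.3 instead gives 8 further weeks after week 58, that is week 66, which is 14 weeks after week 52 and outside the window.
- An unscheduled draw close to weeks 52 and 58.
- A screening draw, a repeat of it and the week 0 draw, if all fall within 12 weeks. Screening may span 40 weeks (section 8.2) or 52 weeks (section 3.1), and one of the screening and week 0 samples can be omitted.
- A late discontinuation draw followed by later draws, which section 11.4 does not guarantee.

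**5. NIH comparison.** A total of 5 ml/kg over 12 weeks is below 9.5 ml/kg over 8 weeks, and it keeps any single draw within 5 ml/kg. In adults 30 mL is below 550 ml, and 5 ml/kg is below 10.5 ml/kg. This half of the statement is correct.

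**The case against.** The best defence is that the 30 mL ceiling makes actual collection conservative whatever the per-kilogram figure says. Much of this stands. A single draw is within 3 ml/kg from 10 kg, and the scheduled pair is within it from 20 kg. A participant reaching week 52 is at least about 8 years old, 30 mL is a maximum, and at 18 kg the excess from two full draws is 6 mL in total. Nothing in the documents shows that such a participant will be enrolled. The defence does not rescue the sentence, because both limits apply to the 12-week total and the number of draws is not capped.

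A second defence is that one figure is a slip and that the IRB, which knows its own limit, sees both numbers side by side. That may be so, but the documents do not show which figure is wrong, and either way the text needs correcting.

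A reader might go further and infer that participants will be bled 67% above the IRB limit. The 67% compares two written caps; it is not a planned volume. A reader might also add a fourth full draw, which would move the threshold to 40 kg. The schedule gives no ordinary route to four draws in 12 weeks: that would take week 64 on the 84-day edge plus an unscheduled draw, or more than one screening repeat. No volume is stated for unscheduled or discontinuation draws either.

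**Conclusion.** The statement is wrong as printed: a cap of 5 ml/kg is not more conservative than 3 ml/kg over the same 12 weeks. That conclusion needs no assumption. The practical reach is narrow. Assuming full 30 mL draws, the rule permits totals above the cited IRB limit below 20 kg on the scheduled week 52 and week 58 draws, and below 30 kg if a contingent third draw falls in the same window. Whether any participant is that light, and whether full volumes would be taken, cannot be told from the documents. Any excess stays within the cited NIH limits. The documents do not support reading this as an actual breach of the IRB limit, since the true limit lies outside them, nor as a threat to the sample size, power or primary week 52 comparison. It should still be fixed, because it is a participant-protection figure in a trial that enrols children.

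**What to change.** Confirm the IRB limit first.

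If it is 3 ml/kg over 12 weeks, replace the cap in section 9 with: *no more than 30 mL at any one draw and no more than 3 ml/kg in total research blood over any 12-week period*. Leave clinically necessary draws outside this cap, so that the rule cannot block a sample needed after a reaction. The comparison sentence should then say that the cap equals the IRB limit and lies below the NIH limits.

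If the IRB figure is misquoted, correct that figure and the claim of being more conservative.

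The cost is one query to the IRB and one or two sentences. With a 3 ml/kg cap the 12-week research maximum is 3 × 18 = 54 mL at 18 kg, 60 mL at 20 kg, 75 mL at 25 kg and 90 mL at 30 kg. At 18 kg, for example, a 30 mL draw at week 52 would leave 54 − 30 = 24 mL for week 58. The downside is smaller research draws, and so fewer secondary or exploratory assays, in the lightest participants only.
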